2. EXTERNAL IRB REVIEW HISTORY*

N/A

3. PRIOR APPROVALS:

Conflict of Interest (COI):

The PI ([name]) is a co-inventor on a patent for the stochastic vibratory stimulation (SVS) mattress device, which will be used in this project. There is an approved mitigation plan in place at UMass due to a potential financial conflict of interest.

COI Mitigation Approval Letter uploaded on eirb.

Clinical Engineering Department:

Medical and research devices with power sources will be inspected for safety, including grounding and minimal current leakage as necessary, prior to being placed in service and will be inspected annually by the Clinical Engineering Department. The Clinical Engineering Department Electrical Safety Inspection protocol shall be used as the inspection procedure. All measurements shall meet the NFPA 99, IEC 60601 healthcare standards for electrical safety. All medical devices with power sources regardless of ownership shall be inspected for safety, including grounding and minimal current leakage as necessary, prior to being placed in service.

Upon receiving new equipment with power sources for use in the study, a study investigator will notify the Clinical Engineering Department at [contact] directly, or through the Materials Management Department, regardless of the purchase rental, loan, lease, evaluation, or demonstration arrangement. The outside manufacturers/ contractors are responsible for the quality and performance of all rented, leased, contracted, or equipment on evaluation.

Biohazardous Agents:

- N/A

Radiation:

- N/A

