Standard measurements and recordings. Physiologic recordings with and without electroencephalographic (EEG) activity will be obtained through state-of-art acquisition system (e.g., Embla, Nihonkohden or other) obtained (hardcopy) or recorded (digital) directly from hospital monitor (e.g., Philips, ixTrend or other). Respiratory inductance plethysmography (RIP) will be used to measure breathing. Respiratory belts will be placed around the chest wall and/or abdomen to record respiratory muscle movements, and allow for detection of inter-breath intervals (IBI) of respiration. Sensors over the skin surface of the torso will be used to record electrocardiographic activity (ECG), and allow for detection of R-R intervals of the ECG signal (index of inter-beat heart rate). Electrodes over the head and face area will be used to measure EEG activity at the surface of the cortex to allow for sleep stage classification using EEG signal analysis; electrode impedance will be measured to help ensure data quality. A probe attached to the foot or wrist will measure arterial-blood oxygen concentration; quality of the plethysmographic activity characterized in the pulse signal will allow for identification of movement periods. Movement periods will be assessed further via actigraphy with a wireless sensor worn around the infant's leg and/or arm that records limb movement. Skin temperature will be measured continuously with a sensor placed under the armpit or back. A sound and light meter placed near the head will record sound frequency and intensity, and changes in light level. Overt behavioral data will be recorded using a camera with a wide-angled lens placed within or near the subject's bed. Medical history (including toxicology screens) and demographic data will be obtained on the infant/child and on the biological mother by manual medical record review or electronically extracted via UMCCTS Data Lake.

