Data acquisition, recording and archival. Physiological data will be digitally recorded (~50-1kHz samples per channel) using bedside data acquisition system or recorded directly from hospital bedside monitor onto secure research computer/laptop. Acquisition systems enable fully synchronized recordings of physiological signals, audiometry, photometry and digital video images. Comments regarding routine nursing assessments and other relevant information (e.g. feeding, pharmacological dosing) will be typed and time stamped along with the physiological data stream. Movement will also be digitally recorded independent of the full-acquisition system using wireless actigraphy sensor. All signals, video images and germane data (e.g., medical histories) will be stored on encrypted, password protected computers. Investigators will also manually record relevant study information (timing and mode of experimental conditions, nursing assessments, feeds, medications etc) on log sheets. A log (computer or pen and paper) of the infant's/child's daily activities and nursing interventions will also be obtained, along with relevant clinical information (feeds, withdrawal scores, medications) obtained from electronic medical record for the study session day

NCT03881553 Study Protocol and Statistical Analysis Plan

and up to one day preceding and following each study session.

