Sessions will begin during the infant's/child's feeding, assessment or wake period, during which time sensors for the full-physiology/polysomnography recording will be applied by research study staff; sessions may begin any time if recordings are obtained directly from the bedside monitor. Periods of no intervention (NEATCap device OFF or SVS Mattress OFF) will be alternated with periods of intervention on (NEATCap device ON or SVS Mattress ON). The duration of each intervention period will conform to the routine care of the study subject. Because feeds vary as a function of subject's age, for example premature infants are typically on a fixed ~every 3-4 hours, whereas older infants and children may feed ad-libitum (i.e., as the child desires), the duration of intervention ON and OFF will vary within and between sessions and among subjects. The hospital standard of care for an individual subject, and the subject's sleep/wake cycle will determine the duration of the intervention periods. For subjects who may sleep throughout the night, periods of intervention will conform to either a routine assessment or medication interval (typically ~ every 3-4 hours) to allow for comparisons between intervention ON and intervention OFF with minimal disruption to the subject. The OFF-ON alternating cycles allow subjects to serve as their own control and ascertain if intervention ON leads to consistent, positive responses in the same subject, and assess whether the effect changes over the period.

NEATCap Intervention: At feed/assessment/wake period preceding a

NCT03881553 Study Protocol and Statistical Analysis Plan

NEATCap ON period, the NEATCap device will be fitted and placed on the child by research study staff. The NEATCap device will be removed (OFF) and replaced (ON) at alternating intervals throughout the study session. Physiological data will be recorded throughout the session while the subject is in the crib/bed or hospital-issued sleeping environment (e.g., motorized seat).

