SVS Mattress Intervention: At the start of the study session (during a feed/nursing intervention/wake period), the subject's hospital mattress will be replaced or covered with the SVS mattress. For bedside studies in babies cared for in infant crib-warmers that have low guard walls, SVS mattress bedframe extenders (Cofab Design, LLC) will be attached to the guard walls of the infant crib-warmers for the duration of the study session. These bedframe extenders will extend the guard wall 2 inches, the height difference between the SVS mattress and the standard crib-warmer mattress. The study staff will turn the external mattress controller off (SVS Mattress OFF) and on (SVS Mattress ON) at alternating periods throughout the study session. Physiological data will be recorded throughout the session while the subject is in the crib/bed with the SVS mattress.

- *Data to be Collected*: Infant/Child subject and biological maternal medical histories including maternal drug use during pregnancy (if applicable), infant/child daily clinical care measurements (feeds, medications, withdrawal scores), and analyzed data (i.e., scored sleep studies; actigraph and physiological data) comprise the data obtained from subjects. Data may be obtained directly from infant/child medical record, maternal medical record, and/or questionnaire administered to person/s providing informed consent. All data will be collected solely for the proposed research studies.

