6. DATA ANALYSIS AND MANAGEMENT*

Statistical Procedures and Power Analysis.

Study design will allow systematic quantification (mean and variance) of the effects of NEATCap device and SVS mattress on automatic function, such as breathing (IBI), cardiac rhythm (R-R), frequency and duration of body movements (e.g., defined via streamlined video, artifact in pulse-oximeter plethysmographic activity, and actigraph count), blood oxygenation (e.g., durations<85%), skin temperature, and sleep states. Analyses will be conducted to determine whether interventions impinge on neural oscillators that drive breathing and cardiac control, and whether NEATCap device reduces dangerous levels of environmental noise, to improve autonomic function and sleep activity.

NCT03881553 Study Protocol and Statistical Analysis Plan

Signal processing algorithms will be used to characterize separately the instability of physiological signals, such as respiration and heartbeat. We will explore, for example, whether different durations of movement periods (e.g., 1.5-5 sec; >5 sec; >10sec) have unique relationships with withdrawal (NAS or iatrogenic) or prematurity, and are affected differently with different interventions (NEATCap device and SVS Mattress).

Parametric tests will be used for analyses of all continuous variables. The Friedman's and Wilcoxon signed-rank tests will be used for nonparametric analyses. For analyses of parametric data separate repeated measures ANOVAs will test effects of stimulus condition (ON or OFF) and trial order. Post-hoc pairwise t-tests will determine differences in responses for conditions of stimulation ON and OFF. For example, separate repeated measures ANOVAs will test effects of stimulus condition (ON or OFF) and trial order on physiological variables. Time of intervention (e.g., infant age, severity of NAS) will be a covariate to assess whether there are critical periods in infant development for optimizing the intervention as a therapeutic strategy. Pearson product-moment correlation coefficient analysis will be used to establish associations between breathing stability (IBI variance) and movement duration, with the expectation that greater variance in respiratory parameters will be positively correlated with excessive movement. *P* values of <0.05 will be considered significant.

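### The plan does not say who scores sleep and video movement, or whether scorers are masked to ON/OFF

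*Combined protocol and SAP*

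**What the plan says.** **Who knows the condition.** Section 4 has research staff operate both devices. For the cap: "the NEATCap device will be fitted and placed on the child by research study staff". For the other device: "The study staff will turn the external mattress controller off (SVS Mattress OFF) and on (SVS Mattress ON) at alternating periods throughout the study session". Under data acquisition it adds: "Investigators will also manually record relevant study information (timing and mode of experimental conditions, nursing assessments, feeds, medications etc) on log sheets".

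**What is scored.** Section 4 lists among the data to be collected "analyzed data (i.e., scored sleep studies; actigraph and physiological data". Sleep staging comes from EEG electrodes placed "to allow for sleep stage classification using EEG signal analysis"; whether that is done by a reader or by software is not stated. Section 6 gives three sources for body movement: "defined via streamlined video, artifact in pulse-oximeter plethysmographic activity, and actigraph count". None is named as the main one.

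**Interest in the result.** Section 3 discloses that the PI "is a co-inventor on a patent for the stochastic vibratory stimulation (SVS) mattress device". It continues: "There is an approved mitigation plan in place at UMass due to a potential financial conflict of interest". The plan's content is not in the documents.

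**What is absent.** Nothing in the text names the scorer of sleep or video, masks a scorer or analyst to ON/OFF, or provides for a second reader or a check of agreement between readers.

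**The concern.** Each child is his or her own control, and Section 6 tests ON against OFF with repeated measures ANOVA and pairwise t-tests. This design removes stable differences between children. It also removes a scorer's constant habit, such as calling too much sleep throughout, because the habit appears in both conditions and cancels.

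It does not remove a leaning that depends on the condition. If a reader who knows that the device is on resolves doubtful epochs towards sleep or stillness, that shift adds directly to the ON-OFF difference. The expected direction is known in advance, since Section 4 says the alternating cycles are meant to show whether the device produces consistent benefit. More children narrow the standard error but leave the shift in place, so a false positive becomes more likely.

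At stake is the credibility of any positive sleep or video-movement result. For the mattress, the first question would be whether the scoring was independent of a team led by its co-inventor.

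**Working it through.** **1. What is exposed.** Setting the outcome sources side by side:

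- Sleep states: exposed if a person stages them. The word used for the sleep studies suggests a reader; the reference to EEG signal analysis leaves software possible.
- Movement from video: exposed if a person reads it.
- Movement from the actigraph or from oximeter artifact: not exposed in the same way.
- Respiratory and heartbeat instability: handled by signal-processing algorithms (Section 6), so not exposed in the same way.
- Oxygenation and skin temperature: instrument readings.

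**2. Inputs for an illustration.** The documents give no sample size, SD, effect size or power, so there is no figure of the plan's to reproduce.

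- Significance level 0.05 (Section 6); two-sided is assumed.
- Period length 3.5 h = 210 min: assumed, the midpoint of the roughly 3-4 h care interval in Section 4.
- SD of the per-child ON-OFF difference in sleep time: assumed 20 min, range 15-30 min.
- Children: assumed n = 20, with n = 40 for comparison.
- True device effect: zero.
- Condition-dependent leaning: assumed 0.5%, 1%, 2% or 5% of scored time, the same in every child.

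**3. Formula.** With leaning b in minutes, the paired t statistic follows a noncentral t distribution with n − 1 degrees of freedom and noncentrality δ = (b / SD) × √n. The false-positive rate is P(|T| > t₀.₉₇₅,ₙ₋₁). For n = 20 the critical value is 2.093.

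Worked case, 2% leaning: b = 0.02 × 210 = 4.2 min; b / SD = 4.2 / 20 = 0.21; δ = 0.21 × √20 = 0.94; rate 14.5%.

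**4. Results.**

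| Leaning | Minutes | n = 20, SD 20 | n = 20, SD 30 to 15 | n = 40, SD 20 |
|---|---|---|---|---|
| 0 | 0 | 5.0% | 5.0% | 5.0% |
| 0.5% | 1.05 | 5.6% | 5.3% to 6.0% | 6.2% |
| 1% | 2.1 | 7.3% | 6.0% to 9.1% | 9.9% |
| 2% | 4.2 | 14.5% | 9.1% to 22.1% | 25.4% |
| 5% | 10.5 | 60.6% | 31.8% to 84.4% | 89.9% |

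**5. Reading the table.** Very small leanings do little harm. From about 2% upward the rate is well above nominal, and it rises with n. The model uses one ON-OFF difference per child. Averaging several pairs of periods would lower the SD and leave a constant leaning unchanged, so the simplification does not exaggerate the problem in that respect.

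**The case against.** The strongest reply is that the documents show silence, not a fault. Five parts of it deserve an answer.

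- *A reader might infer that the bedside team does the scoring.* No section says so. Recording when the condition changed is necessary for any ON/OFF analysis, and the log-sheet sentence does not show that scorers see the log. Sections 5 and 7 also allow data to go to outside collaborators for analysis. This stands: shared scoring is a possibility, not a finding. However, the sharing provisions remove the child's identity, not the condition, so they do not supply masking.
- *Staging may be automated.* It may. If the plan said so, the sleep part of the point would fall away.
- *The conflict of interest is already managed.* An approved plan exists, and a reader should not infer that the interest is unmanaged. Because its content is not shown, it cannot be credited with masking or with keeping the PI from scoring. The disclosed patent interest concerns the mattress only; the documents state no such interest in the NEATCap.
- *Most outcomes are instrumental.* This stands. No outcome is named primary, so nothing shows that scored sleep or video carries the main conclusion.
- *The percentages rest on chosen inputs.* This stands too. A 5% leaning is 10.5 minutes in every 3.5 h period in every child, which is not small, and a uniform direction across children is itself an assumption.

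**Conclusion.** The point holds in a limited form. The plan permits condition-aware human scoring of sleep and video movement in an own-control comparison, and contains no safeguard against it. A condition-dependent leaning would pass undiminished into the ON-OFF contrast.

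The size cannot be determined from the documents. Under the stated assumptions at n = 20, the false-positive rate runs from near nominal (5-6% for a 0.5% leaning, 6-9% for 1%) to clearly inflated (9-22% for 2%, 32-84% for 5%) across SDs of 15-30 min. These figures show how the rate depends on the leaning; they do not estimate what this trial will suffer.

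The documents do not support concluding that scoring will be biased, or that the device results as a whole are compromised. The case for acting is that the safeguard is cheap and the gap is easily closed before scoring.

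**What to change.** In Sections 4 and 6, name who scores sleep stage and video movement, say whether each is done by a person or by software, and add that any human scoring follows these rules:

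- Recordings are cut into coded period files and scored in shuffled order.
- The ON/OFF log is withheld until scoring is locked, as are any typed bedside comments that reveal the condition.
- The audio and sound-meter channel is withheld too, because the mattress makes sound (Section 4 sets a limit on its level) and sound is recorded in synchrony with the other signals.
- The PI does not score. If the mitigation plan already requires this, say so.

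The mattress stays under the child in both conditions, so its EEG and video can largely be masked this way. The cap is visible on video, so for NEATCap score sleep from EEG without video and take movement from the actigraph or oximeter-artifact measure already planned.

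**Cost.** File coding and handling time, and a line in the scoring procedure; the same scorers can do the work. NEATCap video is not used for the main movement measure. Mattress masking may remain incomplete if vibration shows in the recorded signals, and the report should say so if it does.

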4. PROCEDURES INVOLVED

Randomization: Subjects will participate in up to four study sessions that include NEATCap intervention and/or SVS mattress intervention based on duration of subject's hospitalization, availability of research personnel, availability of device and fit-ability of the device around the head and ears of the subject (currently we have 4 sizes, but additional sizes may become available during the study period). Subject will serve as his/her own control, and will receive alternating periods of intervention ON vs intervention OFF.

NCT03881553 Study Protocol and Statistical Analysis Plan

- **Devices: Purpose of use and regulatory approval status (see also section 32).** The two experimental devices used in this study are Abbreviated IDEs:
 - 1) **NEATCap Device:** The NEATCap (“Dreamies”) device is an experimental device engineered by NEATCap, LLC (patent pending). It is a circumaural passive noise protection device comprised of a soft fabric headband with a specially-designed ear covering that simulates the acoustic filtering of a pregnant mother’s body. The device was designed to dampen unsafe, high frequency noises (e.g., alarms from medical equipment) while allowing passage of low frequency sounds such as a caregiver’s voice. There are no electrical components to this device. The device is a circumaural hearing protector, FDA product code EWE [510(K) exempt device], which as per FDA rulings does not require IDE to test before the device is marketed;
see:
<http://www.accessdata.fda.gov/scripts/cdrh/cfdocs/cfPCD/classification.cfm?ID=EWE>. The predicate device for NEATCap “Dreamies” is MiniMuffs Neonatal Noise Attenuators, marketed by Natus Medical since 1995 that has been used on NICU infants in high-noise situations for many years. Indications for use state “The device is intended for use on newborns to provide reduction in the sound level reaching the newborn’s ears.” The proposed studies in this docket involves non-invasive measurements with NEATCap device, also an EWE circumferential hearing protector device, for up to four session periods, not to exceed 24 hours in any one period.

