 - 2) **SVS Mattress Device:** The SVS mattress device is an experimental device. It will be used to gently stimulate the subject. The specially-constructed mattresses are similar to the usual hospital mattress except that inside the mattress foam there is a device that vibrates the foam, controlled by an external unit. The mattresses are constructed by Cofab Design, LLC or other contracted company using patent specifications, modified to adjust for various size cribs and beds. The device components in the mattress and external control unit may be modified with improved technologies to allow for testing of various displacements and mattress sizes, and to help ensure consistency of mattress integrity over time. The mattresses are designed so that the foam vibrates throughout the entire mattress. We are aware of no deleterious effects of the SVS mattress. We have studied over 100 premature infants (since 2001) and over 50 infants exposed to opioids *in utero* (since 2010) using the SVS mattress without incident or apparent side effects. The FDA has not approved the SVS mattress as a treatment for prematurity or withdrawal. Sound level produced by the mattress will be monitored and will not exceed 75 decibels (60-70 dB is normal conversation; 75 dB is about the sound of an average car interior on a highway). The UMass/Memorial Health Care Biomedical Engineering will certify the electrical safety of the mattress devices.
- **Research procedures:** Subjects will participate in up to four sessions, applying either the NEATCap and/or SVS mattress. Sessions will last on average between 8 and 12 hours, and will not exceed 24 hours in any one session. All sessions will

NCT03881553 Study Protocol and Statistical Analysis Plan

be performed at the subject's NICU/CCN or PICU/PIU bedside. Infants and children enrolled in this study will receive routine, standard of care, which may include pharmacological management as prescribed by their primary medical caregiver complementary to the intervention (NEATCap; SVS mattress). Nurses are instructed to provide routine care and to intervene as they would typically do despite the presence of an investigator by the bedside.

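### ON and OFF alternate on a care clock with no counterbalanced start, so doses given at about twice the period length can all fall in one condition, and the analysis does not use the logged dose times

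*Combined protocol and SAP*

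**What the plan says.** Section 4, under its Randomization label, says that each child "will receive alternating periods of intervention ON vs intervention OFF". It describes no random element in which condition comes first. The Study Sessions text gives the rationale: "The OFF-ON alternating cycles allow subjects to serve as their own control".

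That text ties period length to routine care. Premature infants are described as usually fed on a fixed schedule of about 3-4 h. A further rule is limited to one group ("For subjects who may sleep throughout the night"), for whom "periods of intervention will conform to either a routine assessment or medication interval (typically ~ every 3-4 hours". In general, "the duration of intervention ON and OFF will vary within and between sessions and among subjects", because older infants and children may feed on demand. A session usually lasts 8-12 h, starting at about 8 am or 8 pm, and occasionally runs to 24 h.

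During sessions children receive routine care, "which may include pharmacological management as prescribed by their primary medical caregiver complementary to the intervention". Care events are captured as they happen ("e.g. feeding, pharmacological dosing) will be typed and time stamped along with the physiological data stream").

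Section 6 states that "separate repeated measures ANOVAs will test effects of stimulus condition (ON or OFF) and trial order". It adds a covariate for time of intervention, illustrated by infant age and severity of neonatal abstinence syndrome (NAS). It describes no dosing term, dosing-based exclusion window or dosing-based sensitivity analysis.

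**The concern.** Using each child as his or her own control removes differences between children that stay fixed. It does not remove an exposure that changes within the child in step with the device. If a scheduled opioid or sedative is always given in OFF periods and never in ON periods, or the reverse, the ON-OFF contrast contains the difference between early and late drug level as well as any device effect.

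The outcomes in section 6 are breathing, cardiac rhythm, movement, oxygenation, temperature and sleep. Opioids and sedatives act on several of these. The study includes children in withdrawal, some of whom are likely to be on such drugs. In treated children the drug contrast could mimic, mask or reverse a device effect. Although the data needed to detect this are collected, the analysis plan does not use them.

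**Working it through.** **The plan's own figure.** The heading in section 6 mentions a power analysis, but the section gives no sample size, effect size, standard deviation or power. There is nothing to reproduce.

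**Inputs.** From section 4: period length L of 3-4 h; session length T of 8-12 h, at most 24 h; strict alternation. This gives between 8/4 = 2 and 12/3 = 4 periods in a usual session. Assumed, because the documents are silent: dosing interval D, half-life h, number of children n, share affected, and size of the drug effect. OFF first is also an assumption. The plan's wording of OFF-ON cycles suggests it but does not make it a rule.

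**Step 1: where the doses fall.**
- L = 3, D = 6, T = 10, doses at 0 and 6 h. OFF covers 0-3 and 6-9 h; ON covers 3-6 h and the partial 9-10 h. Doses: OFF 2, ON 0.
- L = 4, D = 8, T = 12, doses at 0 and 8 h. OFF covers 0-4 and 8-12 h; ON covers 4-8 h. Doses: OFF 2, ON 0.
- Over 24 h the counts are 4 and 0 (L = 3, D = 6) or 3 and 0 (L = 4, D = 8).
- With D = 2L, each dose falls exactly two periods after the last, so all doses share one condition whatever the time of the first dose.
- With D = L, every period holds one dose. Full separation never occurs; over 12 h at L = 3 the count is 2 and 2.
- In a 12 h session with other intervals, all doses fall in one condition for 75% of possible first-dose times at L = 3, D = 8; for 33% at L = 4, D = 6; and for 100% at D = 12, because there is only one dose.

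**Step 2: difference in drug level.** Take steady state, bolus dosing at the start of a period, first-order elimination and D = 2L. The level in the second half of the dosing interval is the first-half level multiplied by 2^(-L/h), so the ratio of means is 2^(L/h).

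| Half-life h | L = 3, D = 6 | L = 4, D = 8 |
|---|---|---|
| 2 h | 2.8 | 4.0 |
| 4 h | 1.7 | 2.0 |
| 8 h | 1.3 | 1.4 |
| 24 h | 1.09 | 1.12 |

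A dose later in the period lowers the ratio, which tends to 2^(-L/h) as the dose nears the end of the period. Time since last dose is therefore more informative than whether a dose fell in the period.

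**Step 3: does the model absorb it?** Age is essentially constant across the periods of one session. A severity measure entered as time of intervention does not follow dose timing. Trial order does not help either. If it means cycle number, it is crossed with condition and leaves the ON/OFF difference untouched. If it means period number and all sessions start OFF, condition is a function of it.

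**Step 4: possible effect on the test.** A paired t-test at two-sided 0.05 was simulated with no device effect (20,000 runs). The drug contrast is in SDs of the ON-OFF difference, and doses fall in the same condition in every affected child.

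| Share affected | Contrast | n = 20 | n = 40 |
|---|---|---|---|
| 25% | 0.25 | 0.06 | 0.07 |
| 50% | 0.5 | 0.18 | 0.32 |
| 100% | 0.5 | 0.56 | 0.87 |

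The mean bias is share times contrast, for example 0.5 × 0.5 = 0.25 SD. With the direction randomised per child, the rejection rate was 0.048-0.053 throughout and the mean bias about 0.

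**The case against.** A reader might infer that the night-sleeper rule itself ties doses to one condition. It does not. Where periods follow the medication interval, each holds one dose of that drug, so ON and OFF are balanced apart from an odd number of periods. The problem arises where periods follow assessments or feeds, or for a second drug on a longer interval. The rule also covers only children who sleep through the night, and varying periods in children fed on demand weaken any fixed pattern. These objections stand. Fixed-fed premature infants and night sleepers remain exposed.

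A second objection is that dose times relative to session start may differ between children. If they were spread evenly, the average OFF-minus-ON dose count over four 3 h periods would be 0. That is possible, but sessions start at about fixed clock times and begin around care events, so the plan does not ensure it.

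Third, the ratios in step 2 are drug levels under a simple bolus model, and at a 24 h half-life they are small. They should not be read as changes in breathing, movement or sleep.

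Finally, a reader might infer a further distortion from as-needed doses given when symptoms are worse. No part of the documents mentions as-needed dosing, so that claim has no support here. Cutting the data at the first such dose could itself add selection bias.

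**Conclusion.** The point holds in a limited form. Alternation on a care clock without a counterbalanced start allows every scheduled dose to fall in one condition when dosing is at about twice the period length or there are only one or two doses in a session. Nothing in the section 6 model would remove the resulting contrast, although the dose times are available.

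That the analysis omits dose timing is certain from the text. How often doses and conditions coincide cannot be derived, because dosing intervals, half-lives and the share of children treated are not given. Under the assumptions shown, the drug-level ratio is about 1.1 to 4. The false-positive rate ranges from close to the nominal 0.05 to well above it, depending mainly on how many children are affected in the same direction. The documents do not support saying that the trial's contrast is biased, only that the plan leaves it unprotected. The change should be made.

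**What to change.** 1. In section 4, randomise or counterbalance the starting condition (ON first or OFF first) for each child, and reverse it in any later session with the same device. This matters most, because many children may have only one session per device. Only the device switch moves; no dosing changes. Drug and device remain mixed within a single session, but the direction no longer favours one condition across children.
2. In section 6, add one period-level covariate from the logged dose times to the ON/OFF model, such as time since the last scheduled dose of an opioid or sedative. Fit it as a mixed model so that the covariate can vary between periods. State that it cannot separate drug from device in a session where doses follow ON/OFF exactly.
3. As sensitivity analyses, repeat the ON-OFF contrast in children on no such drug, and in ON and OFF periods matched on dose timing.
4. At most, describe any unscheduled doses by condition, without adjusting for them.

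The cost is SAP wording, a derivation from logs already kept, one degree of freedom for the covariate, and a constrained starting order for the device.
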